6.15. Health Outcomes

The patient-reported outcome questionnaires will be analyzed using the mITT population on the EAS, unless specified otherwise.

Item-level missingness is dealt with as per the instrument developers' instruction.

Additional psychometric analyses will be performed by Global Patient Outcomes Real World Evidence at Lilly and documented in a separate analysis plan.

6.15.1. Patient Global Impression of Status for Physical Activity

The counts and percents of participants for Patient Global Impression of Status for Physical Activity (PGIS) response categories at each time point will be summarized by nominal visit and by treatment. For time points >72 weeks, only the participants with prediabetes at randomization will be included so that the denominator for percents will be participants with prediabetes at randomization only. A shift table from baseline to postbaseline of 5 PGIS response categories will be created at each postbaseline visit.

6.15.2. Short-Form-36 Health Survey Version 2, Acute Form

Per copyright owner, the QualityMetric Health Outcomes™ Scoring (PRO_CoRe V2.0) Software will be used to derive the following domain and component scores:

- Mental Component Score (MCS)
- Physical Component Score (PCS)
- Physical Functioning domain (PF)
- Role-Physical domain (RP)
- Bodily Pain domain (BP)
- General Health domain (GH)
- Vitality domain (VT)
- Social Functioning domain (SF)
- Role-Emotional domain (RE), and
- Mental Health domain (MH).

The following analyses for the actual value and change from baseline value for each domain and component score will be conducted:

- descriptive summaries by treatment group, and
- analysis described in [Table GPHK.6.4](#), [Table GPHK.6.5](#), and [Table GPHK.6.6](#).

If data allowed, analysis for SF-36 physical function domain score analysis described in [Table GPHK.6.4](#), [Table GPHK.6.5](#), and [Table GPHK.6.4](#) will be conducted to evaluate the treatment effect in participants who have impaired physical function at baseline, which is defined as PGI-S response at baseline of “moderately limited,” “very much limited,” or “extremely limited”. The

empirical cumulative distribution function (eCDF) curves of the change from baseline to Week-72 in SF-36 physical function domain score will be provided by treatment group.

6.15.3. Impact of Weight on Quality of Life-Lite Clinical Trials

The following parameters will be included from IWQOL-Lite-CT:

- IWQOL Lite CT total score (all items: items 1 through 20)
- Physical Function composite score (5 items: items 1 through 3, 16, 17)
- Physical composite score (7 items: item 1 through 5, 16, 17), and
- Psychosocial composite score (13 items: item 6 through 15, 18, 19, 20).

IWQOL-Lite-CT total and composite scores range from 0 to 100, with higher scores reflecting better levels of functioning.

IWQOL-Lite-CT scores are computed according to the IWQOL-Lite scoring rules (Kolotkin et al. 2002) as following:

- Each composite raw score will be calculated if a minimum of 50% of the items for that composite has a non-missing value; the total score will be calculated if a minimum of 75% of all 20 items has a non-missing value.
 - physical composite score: 4 of 7 items
 - physical function composite score: 3 of 5 items
 - psychosocial composite score: 7 of 13 items
 - IWQOL Lite CT total score: 15 of 20 items
- If the minimum required number of items are answered for a composite then:
 - Calculate the average of the valid non-missing responses corresponding to the items in the total or each composite (1 = “never” or “not at all true” and 5 = “always” or “completely true”).
 - The composite score is then calculated by transforming the raw composite score to the 0 (worst)-to-100 (best) metric using the following formula for every participant at each time point:

$$100 (S_{max} - C_{avg}) / (S_{max} - S_{min})$$

- C_{avg} is the raw average score of all nonmissing item responses in the composite; this average must be a number between 1 and 5, inclusive
- S_{max} is the maximum possible raw score value (that is, 5)
- S_{min} is the minimum possible raw score value (that is, 1)
- Inserting the maximum and minimum possible score values, the formula is reduced to $100 (5 - C_{avg}) / 4$.

For total and each composite score, the actual value and change from baseline value following analyses will be conducted:

- descriptive summaries by treatment group and
- ANCOVA analysis described in [Table GPHK.6.5](#) and [Table GPHK.6.6](#).

If data allowed, analysis for IWQOL physical function composite score analysis described in [Table GPHK.6.5](#) and [Table GPHK.6.6](#) will be conducted to evaluate the treatment effect in participants who have impaired physical function at baseline (as defined in Section [6.15.2](#)).

6.15.4. EQ-5D-5L

For the utility score and the Visual Analog Scale (VAS) scores, following analyses of the actual value and change from baseline value will be conducted:

- descriptive summaries by treatment group and
- analysis of covariance described in [Table GPHK.6.6](#).

6.16. Subgroup Analyses

Efficacy subgroup analyses will be guided by the efficacy estimand in EAS.

Subgroup analyses may be done by country to support local regulatory registrations.

6.16.1. Subgroup Analysis of Body Weight Change

Subgroup analyses by the following baseline characteristics will be provided:

- age group (<65, ≥65 years)
- race
- sex
- ethnicity
- region of enrollment (US, outside of US [OUS])
- body mass index group (<30, ≥30 and <35, ≥35 and <40, ≥40 kg/m²), and
- glycemic status at randomization (normoglycemia vs prediabetes).

The outcome measures for the subgroup analyses will include:

- percent change in body weight from randomization at 72 weeks and
- percentage of participants achieving at least 5% body weight reduction at 72 weeks.

For the percentage change in body weight from randomization at 72 weeks, for each subgroup analyses aforementioned, the following 2 models will be conducted:

- Conduct MMRM model on the subgroup only with terms of treatment group, visit, treatment-by-visit-interaction, country/pooled country, sex, and prediabetes status at randomization as fixed effects, and baseline body weight as a covariate. Variance-covariance structure for within-patient errors will be same as Section 6.13.1.1
- Full MMRM model: treatment group, visit, subgroup, treatment-by-visit-interaction, treatment-by-subgroup-interaction, subgroup-by-visit-interaction, treatment-visit-subgroup-interaction, country/pooled country, sex, and prediabetes status at randomization as fixed effects, and baseline body weight as a covariate. Variance-covariance structure for within-patient errors will be same as Section 6.13.1.1.

For the percentage of participants achieving at least 5% body weight reduction at 72 weeks, for each subgroup analyses aforementioned, the following 2 models will be conducted:

- Conduct logistic regression model on the subgroup with terms of treatment group, country/pooled country, sex and prediabetes status at randomization as fixed effects, and baseline body weight as covariate. Missing body weight measurement at 72 weeks will be imputed by the predicted value from MMRM model on the subgroup aforementioned, then the continuous measurements will be dichotomized into status of achieving at least 5% body weight reduction (Yes or No).
- Conduct logistic regression model with terms of treatment group, subgroup, treatment-by-subgroup-interaction, country/pooled country, sex, and prediabetes status at randomization as fixed effects, and baseline body weight as a covariate. Missing body weight measurement at 72 weeks will be imputed by the predicted value from full MMRM model aforementioned, then the continuous measurements will be dichotomized into status of achieving at least 5% body weight reduction (Yes or No).

6.17. Interim Analyses and Data Monitoring Committee

The details for the interim analyses and Data Monitoring Committee (DMC) will be provided in the DMC Charter.

7. Unblinding Plan

Details of the blinding and unblinding will be provided in Blinding and Unblinding Plan document for Study GPHK.

8. COVID-19 Pandemic Impact

This section lists additional statistical analyses that may be performed at the primary database lock and final database lock to assess the impact of COVID-19 pandemic if the data warrants.

8.1. General Consideration

Percentage and count of randomized participants who followed the COVID-19 mitigation plan may be summarized by treatment group. This includes, but not limited to, participants rescreened, procedures conducted via remote visit or mobile home health visit, visits occurred using the extended visit windows, alternative way of investigator product shipment/dispensing, use of a local lab, etc. A listing of randomized participants who followed the COVID-19 mitigation plan may be provided. Similar analyses may be provided by country and by treatment group.

Percentage and count of randomized participants whose study visits were impacted by COVID-19 pandemic may also be summarized. A listing may be provided.

8.2. Exposure

A listing of randomized participants who had study drug temporary interruption due to COVID-19 pandemic may be provided.

8.3. Protocol Deviation

Percentage and count of randomized participants having important protocol deviation related to COVID-19 pandemic will be summarized by treatment.

Percentage and count of randomized participants with protocol deviation related to COVID-19 pandemic may also be summarized by treatment.

A listing of all randomized participants who had important protocol deviation due to COVID-19 pandemic may be provided.

8.4. Patient Disposition

A summary table for all randomized participants that discontinue study or study treatment due to COVID-19 pandemic will be provided by treatment.

A listing of randomized participants who discontinued the study or study treatment due to COVID-19 pandemic will be provided.

8.5. Adverse Events

A listing of randomized participants who had COVID-19 infection, including death due to COVID-19, during the post-randomization period will be provided. A summary table may be provided if deemed necessary.

8.6. Major Depressive Disorder/Suicidal Ideation

The counts and percentages of participants with TEAEs for major depression may be summarized by treatment group using MedDRA PT nested within SMQ by COVID-19 subgroup (that is, participants without impact versus with impact) for SS group.

A participant is defined as impacted by COVID-19 if either one of the following is satisfied:

- no COVID-19 illness, but impacted by quarantine and travel restrictions, clinics closing, visits being canceled, delay or nondelivery of the investigational product, virtual visits, etc.

OR

- with COVID-19 illness.

The suicidal ideation and behavior solicited through C-SSRS may be summarized by treatment group by COVID-19 subgroup (that is, participants without impact vs with impact) for SS group.

8.7. Local Lab

Local lab due to exceptional circumstances will not be brought into the Lilly database at the time of primary database lock and final database lock per data collection system in Study GPHK, even though local laboratory is one of the options in exceptional circumstances. Therefore, this section is not applicable for analysis purpose.

8.8. Missing Data Due to COVID-19

For the primary endpoints and key secondary endpoints, missing data due to COVID-19 will be handled as described in Section 6.13.1.3. In addition, a summary table for participants whose primary or key secondary measurements were impacted by COVID-19 (including missing, collected using alternative options) may be provided. A listing of participants whose primary or key secondary measurements were impacted by COVID-19 (including missing, collected using alternative options) may be provided if deemed necessary.

9. References

- [ADA] American Diabetes Association. 2. Classification and diagnosis of diabetes: standards of medical care in diabetes-2019. *Diabetes Care*. 2019a; 42(suppl 1):S 13-S28. <https://doi.org/10.2337/dc19-S002>
- [ADA] American Diabetes Association. 6. Glycemic targets: standards of medical care in diabetes-2019. *Diabetes Care*. 2019b;42(suppl 1):S61-S70. <https://doi.org/10.2337/dc19-S006>

Appendix 1. Body Composition Assessments via Dual-Energy X-ray Absorptiometry (DXA)

This section is applicable to the participants who are enrolled in the Dual Energy X-ray Absorptiometry (DXA) addendum.

The primary objective of DXA addendum is to demonstrate that tirzepatide (5 mg, 10 mg, and 15 mg combined) QW is superior to placebo in percent change in total body fat mass from baseline to 72 weeks.

Percent change of total body fat mass will be calculated as:

$$\left[\frac{\text{Total body fat mass at 72 weeks} - \text{Total body fat mass at baseline}}{\text{Total body fat mass at baseline}} \right] * 100$$

The secondary objectives include

- To demonstrate that tirzepatide (5 mg, 10 mg, and 15 mg combined) QW is superior to placebo in loss of total body fat mass in kg from randomization to 72 weeks, and
- To assess, for tirzepatide (5 mg, 10 mg, and 15 mg combined) QW, the following parameters, measured at randomization and 72 weeks:
 - Percent change in total body lean mass, and
 - change in total body lean mass in kg.

Percent change of total body lean mass will be calculated as:

$$\left[\frac{\text{Total body lean mass at 72 weeks} - \text{Total body lean mass at baseline}}{\text{Total body lean mass at baseline}} \right] * 100$$

DXA will be performed at the baseline and at the end of 72-week treatment (Visit 21) or ED.

In addition to the primary and secondary outcomes listed above, the following parameters will also be analyzed:

- total body mass (kg)
- total body fat mass (kg)
- total body lean mass (kg)
- percent body fat mass = total body fat mass / total body mass * 100
- percent body lean mass = total body lean mass / total body mass * 100
- fat lean mass ratio = total body fat mass / total body lean mass
- fat lean mass loss ratio = total body fat mass change / total body lean mass change, and
- fat lean mass percent loss ratio = percent change of total body fat mass / percent change of total body lean mass.

Unless otherwise specified, all analyses for the variables measured or derived from DXA will be conducted on all participants who are enrolled in this addendum, randomized, and have at least 1 dose of study drug, with both baseline and at least 1 postbaseline measurement. Baseline is defined as the last non-missing data collected at randomization (prior to first dosing of study drug). Missing data at Week 72 will be imputed using the last observation carried forward method.

Descriptive summary statistics (for example, sample size, mean, standard deviation, min, max, and median) of all parameters above (but not limited to) will be provided by treatment group (placebo, tirzepatide 5 mg, tirzepatide 10 mg, tirzepatide 15 mg, and all tirzepatide doses combined) at baseline and postbaseline visits (for both actual value and change from baseline value).

In addition, summary of demographics and baseline characteristics for participants in the DXA addendum will be provided.

Unless otherwise noted, all tests of treatment effects will be conducted at a 2-sided alpha level of 0.05, and the CI will be calculated at 95%, 2-sided. There will be no multiplicity adjustment.

The ANCOVA model will be used to analyze the continuous outcomes. Each model will include the treatment group (all tirzepatide doses combined and placebo) and corresponding baseline value for the dependent value.

Summary statistics for categorical measures (including categorized continuous measures) will include sample size, frequency, and percentages, if necessary. Logistic regression will be used to examine the treatment difference in binary outcomes if there is a need to adjust for covariates. Otherwise, Fisher's exact test will be used to examine the treatment difference in categorical outcomes.

Appendix 2. Ambulatory Blood Pressure Monitoring (ABPM)

This section is applicable to the participants who are enrolled in the Ambulatory Blood Pressure Monitoring (ABPM) addendum.

The main objective of ABPM addendum is to assess the effect of 5 mg, 10 mg, and 15 mg doses of tirzepatide compared to placebo on mean change from randomization (Week 0) to Week 36 on 24-hour mean HR and 24-hour mean blood pressure (BP) (SBP/ DBP), as measured during 24-hour ABPM.

Ambulatory monitoring of HR and BP will be performed prior to Visit 3 (Week 0; baseline) and again at Visit 12 (Week 36; final measure).

Only the valid readings will be used in the summary and analyses of the ABPM measurements.

The ABPM measurements are downloaded to the ABPM vendor by the study site at the time of the participant visit. The validity of each ABPM recording will be provided by ABPM vendor.

For an ABPM recording session that is valid, all of the individual ABPM measurements that are flagged as valid and were recorded during the first 24 hours of recordings will be used in the analyses. No further editing of the values will be performed beyond the values flagged as invalid by the ABPM machine.

The following ABPM derived measurements will be evaluated:

- Mean 24-hour SBP, DBP, and HR
- Mean daytime SBP, DBP, and HR.
- Mean nighttime SBP, DBP, and HR.
- Dipper and nondipper response. Blood pressure normally has a circadian pattern in which BP drops at night and is higher during the awake hours. This is referred to as dipping. The following equation (Anwar and White 2001) will be used to assess dipping status:

$$(\text{mean daytime SBP} - \text{mean nighttime SBP}) / (\text{mean daytime SBP}) * 100\%$$

Participants will be classified into the following categories based on their dipping status:

- dipper: $\geq 10\%$
- nondipper: 0% to 10%, and
- riser (reverse dipper): $< 0\%$
- Mean 24-hour, daytime, and nighttime BP load. Blood pressure load will be defined as follows (Ernst and Bergus 2002):

- daytime: percent of SBP readings >140 mmHg and percent of DBP readings >90 mmHg (reported separately)
- nighttime: percent of SBP readings >120 mmHg and percent of DBP readings >80 mmHg (reported separately)
- mean 24 hour: percent above systolic limits (daytime and nighttime combined) and percent above diastolic limits (daytime and nighttime combined)
- Mean 24-hour, daytime, and nighttime pulse pressure (PP)
 - $PP = SBP - DBP$
- Mean 24-hour, daytime, and nighttime mean arterial pressure (MAP)
 - $MAP = (2 * diastolic + systolic) / 3$
- Treatment-emergent abnormally high HR (based on mean 24-hour values) as defined in [Table GPHK.6.11](#).
- Treatment-emergent abnormally high SBP and DBP defined as following (adapted from Pickering et al. 2005):
 - Mean Daytime SBP/DBP: >140/90 mmHg
 - Mean Nighttime SBP/DBP: >125/75 mmHg
 - Mean 24-hour SBP/DBP: >135/85 mmHg

The daytime (0700 to 2200 hours) and nighttime (2200 to 0700 hours, inclusive) definitions will be used to provide accurate estimates of the BPs and heart rates during the awake and sleeping periods.

Mean plots for each derived continuous measurement above by treatment group by visit may be created.

Summary statistics for actual and change from baseline for each derived measurements above will be performed by treatment group and by visit.

Blood pressure load is an indicator of hypertensive burden and has been shown to correlate with markers of cardiovascular morbidity in participants with hypertension and has been used as a method of assessing antihypertensive drug efficacy. Summary statistics of 24-hour BP load for all participants and those with or without hypertension at baseline will be calculated at baseline and at 36 weeks.

In addition to these derived measurements, the following summary measurements that provide information on the individual ABPM recordings sessions will be assessed:

- total duration of recording session
- total duration of recording session in the first 24 hours
- total number of measurements in the first 24 hours

- Number of valid measurements in the first 24 hours, and
- Percent of valid measurements in the first 24 hours.

In addition to the above analyses of outcomes specifically collected through ABPM reading, following analyses may be performed for participants in the ABPM addendum if deemed necessary:

- summary of demographics and baseline characteristics
- summary of concomitant medication at baseline, and
- summary of change in concomitant medication of interest (for example, antihypertensive)

Unless otherwise noted, all tests of treatment effects will be conducted at a 2-sided alpha level of 0.05, and the CI will be calculated at 95%, 2-sided. There will be no multiplicity adjustment.

All analyses for the variables measured or derived from ABPM, will be conducted on all participants who are enrolled in ABPM addendum, randomized and have at least 1 dose of study drug, with both baseline and at least 1 postbaseline measurement.

For continuous outcomes collected from the ABPM, including BP and HR, the analysis will be conducted using an analysis of covariance model, with terms of treatment group (tirzepatide 5 mg, 10 mg, 15 mg, and placebo), baseline measurement, and HR controlling medicine use status at baseline.

For categorical measures (including categorized continuous measures), logistic regression will be used to examine the treatment difference, if there is a need to adjust for covariates. Otherwise, Fisher's exact test will be used to examine the treatment difference.

References

Appendix 3. Searching Criteria for Special Safety Topics

Abuse Liability

To identify AE terms suggestive of potential abuse liability, narrow terms from SMQ of Drug abuse and dependence (20000101) will be used.

Acute Gallbladder Disease

All biliary colic, cholecystitis, or other suspected events related to gallbladder disease will be identified using the MedDRA PTs in any of the following:

- Narrow PTs in Gallbladder related disorders SMQ (20000124)
- Narrow PTs in Biliary tract disorders SMQ (20000125), and
- Narrow PTs in Gallstone related disorders SMQ (20000127).

Amputation/Peripheral Revascularization

Amputations/peripheral revascularization events will be identified using the following MedDRA PTs:

- Amputation
- Peripheral revascularization.

C-cell Hyperplasia and Thyroid Malignancies

Thyroid malignancies and C-Cell hyperplasia will be identified using MedDRA HLT for Thyroid neoplasms and PT for thyroid C-cell hyperplasia.

Hepatic Treatment-Emergent Adverse Events

Treatment-emergent potentially drug-related hepatic disorders will be identified using the MedDRA PTs contained in any of the following:

- Broad and narrow terms in the Liver related investigations, signs and symptoms SMQ (20000008)
- Broad and narrow terms in the Cholestasis and jaundice of hepatic origin SMQ (20000009)
- Broad and narrow terms in the Hepatitis non-infections SMQ (20000010)
- Broad and narrow terms in the Hepatic failure, fibrosis and cirrhosis and other liver damage SMQ (20000013)
- Narrow terms in the Liver-related coagulation and bleeding disturbances SMQ (20000015)

- Narrow PTs in Gallbladder related disorders SMQ (20000124)
- Narrow PTs in Biliary tract disorders SMQ (20000125); and
- Narrow PTs in Gallstone related disorders SMQ (20000127).

Hypersensitivity Reactions

Analyses are based on the following:

- Narrow and algorithm terms in Anaphylactic reaction SMQ (20000021)
- Narrow terms in Angioedema SMQ (20000024)
- Narrow terms in Severe cutaneous adverse reactions SMQ (20000020)
- Narrow terms in Hypersensitivity SMQ (20000214).

For the Anaphylactic reaction SMQ, each term is classified by scope (Narrow, Broad) and by category (A, B, C, D). All Narrow terms are category A, and all Broad terms are category B, C, or D. In addition to the usual Narrow and Broad searches, the SMQ defines an algorithm to further refine the cases of interest. For Time Period A analysis, the Anaphylactic reaction SMQ algorithm will be included. The algorithm is based upon events that occur within Time Period A. The counts and percentages of participants who experienced a TEAE for the following will be analyzed for each of the 2 time periods:

- any narrow term from any one of the 4 SMQs indicated above (that is, combined search across narrow of all 4 SMQs)
- any narrow scope term within each SMQ, separately (that is, narrow SMQ search). For Time Period A analysis, any term from Anaphylactic reaction SMQ algorithm.

Injection Site Reactions

The ISR AE will be identified using the MedDRA PT in any of the following:

- HLT of Injection site reaction
- HLT of Administration site reaction
- HLT of Infusion Site Reactions

Pancreatitis Events

Determination of investigator-reported events will be through the “Acute pancreatitis” MedDRA SMQ (20000022, narrow scope) and a “Chronic pancreatitis” PT search of the AE database, while adjudication-confirmed pancreatitis are found from adjudication forms.

Malignancy

The malignancy events will be identified using the MedDRA PT contained in Malignant tumours SMQ (20000194) narrow scope or Tumours of unspecified malignancy SMQ (20000195) narrow scope.

Major Depressive Disorder/Suicidal Ideation

AEs will be searched using MedDRA PTs from SMQs narrow scope: 20000037 [Suicide/self-injury] and 20000167 [Depression (excl suicide and self injury)].

Metabolic Acidosis, Including Diabetic Ketoacidosis

Metabolic acidosis including diabetic ketoacidosis will be identified using the following MedDRA PTs:

- Diabetic ketoacidosis
- Ketoacidosis
- Euglycaemic diabetic ketoacidosis
- Ketonuria
- Diabetic ketosis
- Diabetic ketoacidotic hyperglycaemic coma
- Ketosis
- Lactic acidosis
- Urine ketone body present
- Blood ketone body
- Blood ketone body increased
- Urine ketone body, and
- Blood ketone body present.

Supraventricular Arrhythmias and Cardiac Conduction Disorders

The supraventricular arrhythmias and cardiac conduction disorders events will be identified using the MedDRA PT contained in any of the following SMQs:

- 1) Supraventricular Arrhythmias:
 - For symptoms: Arrhythmia related investigations, signs and symptoms SMQ (20000051), narrow and broad terms
 - For supraventricular arrhythmias: In Cardiac arrhythmia SMQ, under tachyarrhythmia sub SMQ
 - Supraventricular tachyarrhythmia SMQ (20000057), broad and narrow terms
 - Tachyarrhythmia terms, nonspecific SMQ (20000164), narrow terms only; and
 - Ventricular tachyarrhythmia SMQ (20000058), narrow terms only.

2) Cardiac Conduction Disorders

- Conduction defects SMQ (20000056), narrow terms only; and
- Cardiac conduction disorders High Level Term (HLT; 10000032), all PTs.

Leo Document ID = 4179a915-5987-41e3-8d60-7981e462f8bc

Approver: PPD

Approval Date & Time: 28-Sep-2021 17:47:59 GMT

Signature meaning: Approved

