9.4.4.2. Adverse Events

Adverse events will be coded from the actual term using the Medical Dictionary for Regulatory Activities (MedDRA) and reported with preferred terms and system organ class. Counts and percentages of participants experiencing events will be reported for each treatment group, and Fisher's exact test will be used to compare the treatment groups.

The percentage of participants experiencing TEAE, SAE, discontinuation due to AE will be summarized by treatment group.

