6.14.1.4. Other Serious Adverse Events

The counts and percentages of participants who experienced a SAE (including deaths and SAEs temporally associated or preceding deaths) during the postbaseline period will be summarized by treatment using MedDRA PT nested within SOC. Events will be ordered by decreasing frequency within SOC. The SOC will be in alphabetical order.

A listing of all SAEs will be provided. The listing will include treatment, participant identification including the site number, date of event, age at the time of enrollment, sex, MedDRA SOC and PT, Reported term, severity, outcome, relationship to study drug, time from first dose of study drug to the event, AE start date, AE end date, seriousness, and action taken related to study treatment.

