6.14.3.13. Metabolic Acidosis

This section is applicable for participants developing T2DM during the study treatment (up to primary database lock [72 weeks] and final database lock [176 weeks]).

Severe/serious treatment-emergent metabolic acidosis, including diabetic ketoacidosis will be captured as an AESI.

The counts and percentages of participants with metabolic acidosis, including diabetic ketoacidosis may be summarized by treatment based on searching criteria in [Appendix 3](#).

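### The SAP's search list for the metabolic acidosis AESI has no generic acidosis term, so an event coded under the topic's own name would not be flagged

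*SAP*

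**What the plan says.** SAP 6.14.3.13 sets the scope first: "This section is applicable for participants developing T2DM during the study treatment", at both the primary and the final database lock. It then defines the event of interest: "Severe/serious treatment-emergent metabolic acidosis, including diabetic ketoacidosis will be captured as an AESI". The topic's own summary is worded as optional. The SAP says that counts and percentages of participants with "metabolic acidosis, including diabetic ketoacidosis may be summarized by treatment based on searching criteria in" Appendix 3. The section gives no other search rule.

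Appendix 3 supplies the rule: "Metabolic acidosis including diabetic ketoacidosis will be identified using the following MedDRA PTs". A bulleted list of named preferred terms (PTs) follows. The only entry that is not about ketones is "Lactic acidosis".

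Protocol 9.4.4.2 says how a reported event reaches a PT: "Adverse events will be coded from the actual term using the Medical Dictionary for Regulatory Activities (MedDRA) and reported with preferred terms".

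**The concern.** The AESI is defined by a broad name, and ketoacidosis is stated to be one part of it. The search that puts the definition into practice covers ketone-related terms and lactic acidosis only. If an investigator reports metabolic acidosis without naming a ketone or lactate cause, and the report is coded to a generic term, nothing on the list matches it. The definition says the event is an AESI and the search rule says it is not.

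At stake is the completeness of one safety count. An AESI search exists to gather events that would otherwise be scattered over individual PTs. Few events are likely under this topic, so one unflagged case could be the difference between reporting none and reporting one.

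**Working it through.** The plan gives no figure to reproduce. The check is a term-by-term reading of the list against the definition, followed by a rough size for the population in scope.

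**1. Is the list complete as printed?** Yes. Its next-to-last entry reads "Urine ketone body, and" and is followed by a final entry that ends in a full stop. Nothing suggests a cut or a redaction.

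**2. What is on it?** Grouped by content:

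| Group | Terms | Count |
|---|---|---|
| Ketoacidosis | ketoacidosis; diabetic ketoacidosis; euglycaemic diabetic ketoacidosis; diabetic ketoacidotic hyperglycaemic coma | 4 |
| Ketosis | ketosis; diabetic ketosis | 2 |
| Ketones in urine | ketonuria; urine ketone body; urine ketone body present | 3 |
| Ketones in blood | blood ketone body; blood ketone body increased; blood ketone body present | 3 |
| Lactic acidosis | lactic acidosis | 1 |
| Generic acidosis | none | 0 |

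The total is 4 + 2 + 3 + 3 + 1 = 13 terms, of which 12 are ketone-related and 1 is not. Where the word acidosis occurs, it is inside a cause-specific term.

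**3. Can a generic term enter another way?** Not by the stated rule. Most topics in Appendix 3 use a Standardised MedDRA Query or a high level term, which brings in a group of related PTs. This topic uses named PTs only, and neither document gives a second search for it.

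**4. Where would an unflagged event still be seen?**
- In the tables of treatment-emergent events by PT and by maximum severity (SAP 6.14.1.1).
- If serious, in the serious adverse event table and the full listing (SAP 6.14.1.4: "A listing of all SAEs will be provided"), and in a narrative (SAP 6.14.2).
- If severe but not serious, in the 6.14.1.1 tables. A narrative is planned only if the event led to permanent discontinuation of treatment.

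**5. How many participants are in scope?** Protocol 9.2 assumes 2400 randomized, 60% with prediabetes, and progression to diabetes over 3 years in 6% on placebo and 1.6% on tirzepatide. With 1:1:1:1 allocation:
- prediabetes: 2400 × 0.60 = 1440, that is 360 on placebo and 1080 on tirzepatide;
- progressing: 360 × 0.06 + 1080 × 0.016 = 21.6 + 17.3 = 38.9, or about 39.

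The figure is before the assumed 49% dropout, which would lower the number observed. It leaves out anyone who progresses from normoglycemia, for whom the protocol gives no rate. It gives only the order of magnitude: tens of participants, not the whole trial.

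**The case against.** The best defence is that the list fits the topic's evident purpose and only the label is too wide. The section is confined to participants who develop diabetes, where ketoacidosis and lactic acidosis are natural targets. Metabolic acidosis is not among the AESIs in Protocol 9.4.4.3. The SAP's revision history says its special safety language was aligned with a program-level safety plan, which is not among the documents. On this view the mismatch is one of naming. That is a fair argument about how to resolve the inconsistency, but it does not remove it: 6.14.3.13 names ketoacidosis as only part of the topic.

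The limits on consequence also stand. The topic's own summary is optional (the lead-in to SAP 6.14.3 is firmer on AESIs generally), and the general tables remain.

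A reader might infer three stronger things that the documents do not support:

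- **That the search has zero sensitivity for such events.** The absence of the terms is documented. How MedDRA codes a given report is not, because the dictionary is not reproduced.
- **That isolated ketone findings inflate the AESI.** The AESI is limited to severe or serious events. A ketone finding that is neither can match the list and reach the optional summary, but it is not an AESI.
- **That acidosis after diarrhea or renal impairment is missed across the trial.** Protocol 10.3.1.12 links gastrointestinal events to dehydration and renal deterioration, not to acidosis. In participants who do not develop diabetes, acidosis is outside this topic whatever the list contains.

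**Conclusion.** The point holds as an inconsistency between SAP 6.14.3.13 and Appendix 3. As written, the search does not flag an event coded to a generic acidosis PT, although the definition makes such an event an AESI when it is severe or serious. None of the 13 listed terms is generic.

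The effect is small. It is confined to participants who develop type 2 diabetes during study treatment, and to AESI flagging and one optional summary. Such events are not lost from the safety report, and no primary or key secondary analysis changes.

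The conclusion rests on one assumption: that generic acidosis terms exist as separate PTs in the MedDRA version used, so that a report of metabolic acidosis would be coded there and not to a listed term.

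**What to change.** Bring SAP 6.14.3.13 and Appendix 3 into line.

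- **Preferred:** add *Metabolic acidosis* and *Acidosis* to the Appendix 3 list, after confirming that each is a PT in the MedDRA version in use at each database lock.
- **Failing that:** rename the topic in both places to what the list captures, namely ketosis or ketoacidosis and lactic acidosis, so that the reported count is not read as covering all metabolic acidosis.

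Either is a short SAP edit plus, for the first, an update to the search code. It needs no new data and no change of model. Protocol 9.4.4.3 leaves the detail of AESI analysis to the SAP and does not list this topic, so no protocol amendment appears to be needed.
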